13.3.4. Clinical Function and Quality of Life Measures

The actual scores and changes from baseline in each measure will be summarized using descriptive statistics. Missing data will be imputed using multiple imputation. Multiple imputation will be performed on actual values, domains, total scores, or summary scores depending on the endpoint. In addition, each clinical function measure will be analyzed using an ANCOVA model. The model may include covariates such as corresponding baseline value, baseline NfL, duration from onset of symptoms to the first dose of study treatment, and riluzole or edaravone use. The model will be used to estimate least-square (LS) means for each treatment group with standard errors (SEs), and LS mean differences between treatment groups with corresponding 95% confidence intervals (CIs). The p-values comparing treatment differences will also be presented.

For integrated analyses of Part 1 and Part 2 for Cohorts D1 and D2, treatment groups will be defined as Early-start BIIB105 (i.e., those who initiated BIIB105 in Part 1) and Placebo/Delayed-start BIIB105 (i.e., those who received placebo in Part 1), with baseline defined as Part 1 baseline. Clinical function data will be presented by the 120 mg dose level and treatment group (Cohort D1+D2 Early-start vs Placebo/Delayed-start). They will also be presented by cohort and treatment group as a sensitivity analysis (Cohort D1 Early-start vs Placebo/Delayed-start; Cohort D2 Early-start vs Placebo/Delayed-start).

[figure not shown]

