5.6. Efficacy Endpoints

5.6.1. General Analysis Methods for Efficacy Endpoints

Covariates

The covariates for the statistical models in the integrated analysis for participants from Cohorts D1 and D2 will be based on Part 1 baseline and will be as follows:

- Corresponding baseline score for the endpoint (continuous)
- Baseline disease duration from onset of symptoms to the first dose of study treatment as derived in Appendix 1, i.e. time since symptom onset in months (continuous)
- Baseline plasma NfL
- Riluzole or Edaravone use which will take 3 levels as follows:
 - Edaravone Use (Edaravone = Yes; Riluzole = Yes OR No)
 - Riluzole Only (Riluzole = Yes and Edaravone = No)

CONFIDENTIAL

The information contained herein may not be used, disclosed, or published without the written consent of Biogen MA Inc.

- Neither (Edaravone = No and Riluzole = No)

Edaravone use may only occur for a very small number of subjects in which case this could cause problems for statistical modelling. If Edaravone use is limited to <5 subjects within the relevant population then riluzole and edaravone use will be combined so that there are only 2 levels:

- Edaravone or Riluzole Use (Edaravone = Yes and Riluzole = Yes; OR Edaravone = Yes and Riluzole = No; OR Edaravone = No and Riluzole=Yes)
- Neither (Edaravone = No and Riluzole = No)

Missing data for individual items in scales

The imputation of individual components of each endpoint are described in Section 5.6.2. Imputation will be performed within a scale for each endpoint by prorating the observed scores at the same visit, for example, if there are missing responses to some of the individual questions on a scale at a given visit the endpoint may only be derived for that visit if there are a certain number of individual items/components with available data. Specific details are provided for each assessment/scale, as this differs across assessments/scales. These imputations within a visit will be performed prior to applying imputations on the endpoint at the visit level (e.g. multiple imputation) and will be applied consistently across visits where required. Multiple imputation will not be applied on an individual item/question within an assessment/scale.

Multiple imputation (MI)

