ALSFRS-R Bulbar function Respiratory function Fine motor skills Gross motor skills (Total score will not be imputed separately; instead the imputed datasets from the functional domains will be used to calculate the total score. A separate model will be used for each functional domain.)	8492382
Percent predicted SVC	6734934
HHD megascore (overall, upper extremities, lower extremities)	3748311
[REDACTED]	[REDACTED]
[REDACTED] [REDACTED] [REDACTED]	[REDACTED]
[REDACTED]	[REDACTED]

Imputed values that are outside of the expected range of a scale will be reset: for example, for ALSFRS-R bulbar function should only be in the range 0 to 12. Values outside of this

CONFIDENTIAL

The information contained herein may not be used, disclosed, or published without the written consent of
Biogen MA Inc.

range will be reset so that values below 0 are set to 0 and values above 12 are set to 12. Values will be used as imputed, and will not be rounded prior to analysis.

For each of the 100 imputed datasets, change from baseline will be calculated using the imputed datasets, and the change from baseline endpoint will be compared between treatment groups using an ANCOVA model for continuous endpoints (efficacy and pharmacodynamic endpoints). The ANCOVA model will include covariates for each of the corresponding baseline value for the endpoint, baseline plasma NfL, baseline disease duration since symptom onset, and use of riluzole or edaravone. The model will be used to present overall LS means and standard errors for each treatment group, and LS mean differences for treatment with corresponding 95% CI and p-values. A combined estimate of the LS means, LS mean differences and standard errors of the 100 imputed datasets will be obtained, where standard errors will be used to obtain 95% CI from PROC MIANALYZE [Little et al, 2002]. Separate ANCOVA models will be used to obtain estimates, 95% confidence intervals and p-values for other visits. For subjects who died, the imputed values after death will be used in the ANCOVA analysis eg change from baseline in ALSFRS-R.

For integrated analyses of Part 1 and Part 2 for Cohorts D1 and D2, ANCOVA model will be performed for Early-start BIIB105 120 mg vs. Placebo/Delayed-start BIIB105 120 mg.

Presentation of Data

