The actual scores and changes from baseline in each measure will be summarized using descriptive statistics. Missing data will be imputed using multiple imputation. Multiple imputation will be performed on actual values, domains, total scores, or summary scores depending on the endpoint. In addition, each clinical function measure will be analyzed using an ANCOVA model. The model may include covariates such as corresponding baseline value, baseline NfL, duration from onset of symptoms to the first dose of study treatment, broad ALS/polyQ ALS, and riluzole or edaravone use. The model will be used to estimate least-square (LS) means for each treatment group with standard errors (SEs), and LS mean differences between treatment groups with corresponding 95% confidence intervals (CIs). The p-values comparing treatment differences will also be presented. LS mean changes over time will be also presented in line plots.

For integrated analyses of Part 1 and Part 2 for Cohorts D1 and D2, treatment groups will be defined as Early-start BIIB105 120 mg (i.e., those who initiated BIIB105 120 mg in Part 1) and Placebo/Delayed-start BIIB105 120 mg (i.e., those who received placebo in Part 1), with baseline defined as Part 1 baseline. Clinical function data will be presented by treatment group (Early-Start BIIB105 120 mg vs Placebo/Delayed-start BIIB105 120 mg). They might also be presented by cohort and treatment group as a sensitivity analysis (Cohort D1 Early-start vs Placebo/Delayed-start; Cohort D2 Early-start vs. Placebo/Delayed-start).

CONFIDENTIAL

The information contained herein may not be used, disclosed, or published without the written consent of
Biogen MA Inc.

Due to the washout period between Part 1 and Part 2 for all participants in Cohorts A, B, C1, and C2, Part 2 clinical function data for these cohorts will be presented separately from Part 1. Descriptive summaries will be presented for the combined cohort (A+B+C1+C2) by their initial dose level, i.e. 60 mg in Part 2 with baseline defined as Part 2 baseline. As participants on the 60 mg dose in Part 2 were increased to 120 mg starting December 2023, visits since first dose escalation to 120 mg will not be included in the analysis for Part 2 BIIB105 60 mg.

CONFIDENTIAL

The information contained herein may not be used, disclosed, or published without the written consent of
Biogen MA Inc.

Table 3: Analysis Methods for Part 2 and Integrated Summary of Efficacy and PD Data

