ALSFRS-R total score = average of all answered item scores from other 3 domains x

Descriptive statistics

Descriptive statistics, including ALSFRS-R total and change from baseline in the ALSFRS-R total scores, will be evaluated by visit with descriptive statistics (mean, SD, median, 1st and 3rd quartiles, range) for pooled group DL and Part 2 BIIB105 60 mg in the FAS population.

Spaghetti plots will be presented by treatment group.

Statistical Analyses

The following analyses will be performed for pooled group DL in the FAS population.

CONFIDENTIAL

The information contained herein may not be used, disclosed, or published without the written consent of
Biogen MA Inc.

For integrated analyses of Part 1 and Part 2 for Cohorts D1 and D2, difference between treatment groups (i.e. Early-start BIIB105 120 mg and Placebo/Delayed-start BIIB105 120 mg) in least square means of Week 40 change from baseline with corresponding standard errors and 95% confidence intervals taken from the ANCOVA described in Section [5.6.1](#) based on the multiple imputation dataset.

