5.6.5. Time to Event Analyses

Time-to-event endpoints include

- Time to death or permanent ventilation (≥ 22 hours of mechanical ventilation [invasive or noninvasive] per day for ≥ 21 consecutive days)
- Time to death

CONFIDENTIAL

The information contained herein may not be used, disclosed, or published without the written consent of Biogen MA Inc.

- Time to death, permanent ventilation (≥ 22 hours of mechanical ventilation [invasive or noninvasive] per day for ≥ 21 consecutive days), or withdrawal from study due to disease progression.

Time to event endpoints will be summarized using Kaplan-Meier curves based on randomization in Study 275AS101 Part 1.

Participants without an event will be censored at the last known alive dates, defined as the interim cut date for 275AS101 (March 12, 2024) or as the last date in the database with any actual study visit or measurements indicating their alive status.

Summary of time-to-event data will be presented by treatment group including number of participants with the event (separate by each individual event for composite event) and number of participants who were censored. Kaplan-Meier plots will be presented. The median survival time, percentiles (5th, 10th, 25th, 75th) and associated 95% confidence limits, and proportion of participants with an event at a list of time points (Week 26, 52, 78, etc.) will be estimated using the Kaplan-Meier. Treatment comparison for time to event will be based on a log rank test. A Cox proportional hazards model will be used to obtain the hazard ratio and 95% confidence intervals. The Cox proportional hazards model may include covariates such as baseline disease duration since symptom onset, baseline plasma NfL, and riluzole or edravone use (as specified in Section 5.6.1 under Covariates). P-value from the log rank test of the survival function will be provided. Hazard ratio (and corresponding 95% CI) comparing the treatment group will be obtained from Cox proportional hazard model. The log-rank test may be stratified by median baseline plasma NfL.

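### The integrated D1+D2 ANCOVA is inconsistently specified: the committed covariate lists omit ALS/polyQ status, a later paragraph makes it optional, and the by-cohort sensitivity analysis became optional without being declared (minor)

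*SAP*

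**What the plan says.** **Covariates.** Section 5.6.1 of the Part 2/Integrated SAP describes the integrated model three times.

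- Under Covariates it opens: "The covariates for the statistical models in the integrated analysis for participants from Cohorts D1 and D2 will be based on Part 1 baseline". Four items follow: baseline score, disease duration, baseline plasma NfL, and riluzole/edaravone use.
- Under Multiple imputation it commits the ANCOVA to the corresponding baseline value plus "baseline plasma NfL, baseline disease duration since symptom onset, and use of riluzole or edaravone". These are the same four items.
- Under Presentation of Data it says the model *may* include covariates such as baseline value, baseline NfL, "duration from onset of symptoms to the first dose of study treatment, broad ALS/polyQ ALS, and riluzole or edaravone use". ALS/polyQ is named as a covariate nowhere else in this SAP.

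The last sentence is the one in protocol Section 13.3.4 with one term added. The protocol's list ends "duration from onset of symptoms to the first dose of study treatment, and riluzole or edaravone use" and is also optional.

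**Where the model is used.** SAP Sections 5.6.2 (ALSFRS-R), 5.6.3 (HHD) and 5.6.4 (SVC) each report the treatment difference in "least square means of Week 40 change from baseline with corresponding standard errors and 95% confidence intervals taken from the ANCOVA" of Section 5.6.1.

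**Time to event.** Section 5.6.5 states: "The Cox proportional hazards model may include covariates such as baseline disease duration since symptom onset, baseline plasma NfL, and riluzole or edravone use". It adds: "The log-rank test may be stratified by median baseline plasma NfL". ALS/polyQ is not named in either sentence.

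**By-cohort results.** Of the D1+D2 clinical function data, protocol Section 13.3.4 says: "They will also be presented by cohort and treatment group as a sensitivity analysis". SAP Section 5.6.1 changes *will* to *might*. SAP Section 6 declares two changes from the protocol, both on time-to-event endpoints, and does not list this one.

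**The concern.** Cohort is the unit within which participants were randomised, and the two cohorts used different ratios (protocol Section 5.1.1). Pooling them without a cohort term lets the different polyQ shares of the two arms enter the treatment contrast. Protocol Sections 3.1 and 3.1.1 say polyQ-ALS progresses faster on ALSFRS-R and respiratory vital capacity, so the factor is prognostic for two of the three endpoints concerned. The documents make no such statement for HHD.

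Two programmers could fit different Week 40 models, with and without ALS/polyQ, and each could cite Section 5.6.1. The by-cohort display would show whether the pooled contrast holds within each disease group, but it is no longer promised. SAP Section 3.3 plans no subgroup analyses, so no polyQ-specific efficacy result is committed.

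**Working it through.** **1. Planned counts (protocol Section 5.3.1; sizes for D1 and D2 are approximate).** Active/placebo: A 6/2, B 6/2, C1 9/3, D1 36/12, C2 3/1, D2 12/6. ALS: 8 + 8 + 12 + 48 = 76. PolyQ-ALS: 4 + 18 = 22. The total of 98 reproduces the protocol's figure and its 76/22 split.

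**2. Composition of the pooled arms.** Early-start: 36 + 12 = 48, polyQ share 12/48 = 25.0%. Delayed-start: 12 + 6 = 18, polyQ share 6/18 = 33.3%. Difference: 0.0833.

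**3. Bias without the term.** Let d be the extra polyQ decline, in residual SDs, that remains after the four committed covariates. The documents give no value, so d is assumed at 0.1, 0.25, 0.5 and 1. Bias towards early start = 0.0833 × d.

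**4. SE without the term.** The polyQ mix enlarges the pooled within-arm variance. The within-arm sum of squares for polyQ is 48 × 0.25 × 0.75 + 18 × (1/3) × (2/3) = 9 + 4 = 13, on 64 degrees of freedom. So SE = √[(1/48 + 1/18)(1 + 13d²/64)].

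**5. SE with the term.** Information is 36×12/48 + 12×6/18 = 9.00 + 4.00 = 13.00, so SE = √(1/13.00) = 0.2774 SD. Ignoring cohort, information is 48×18/66 = 13.09. If polyQ has no effect, the cost of the term is √(13.09/13.00) = 1.0035, or 0.35%.

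**6. Test size.** I simulated 400,000 trials per value of d with no treatment effect, fixed polyQ counts and a nominal two-sided 5% t-test.

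| d (SD) | Bias (SD) | SE without term | Bias/SE | Two-sided size | Tail towards early start | Other tail | SE change from adding the term |
|---|---|---|---|---|---|---|---|
| 0.1 | 0.008 | 0.2767 | 0.03 | 5.0% | 2.7% | 2.3% | +0.25% |
| 0.25 | 0.021 | 0.2781 | 0.07 | 4.9% | 2.9% | 2.0% | -0.3% |
| 0.5 | 0.042 | 0.2833 | 0.15 | 4.7% | 3.1% | 1.5% | -2.1% |
| 1 | 0.083 | 0.3032 | 0.27 | 4.0% | 3.2% | 0.8% | -8.5% |

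With cohort in the model, size is 5% and each tail about 2.5% (within simulation error) at every d.

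**7. Precision of the by-cohort results.** D1 only: √(1/36 + 1/12) = 0.33 SD. D2 only: √(1/12 + 1/6) = 0.50 SD. The D2 result would be descriptive.

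**The case against.** The strongest case against is that little depends on this. The bias reaches 0.27 SE only if a full SD of polyQ effect remains after adjustment for baseline score, NfL and disease duration, and nothing in the documents supports so large a shift. At 0.25 SD or less it is at most 0.07 SE. The study was stopped early and the report is abbreviated (SAP Section 1). That section's general remark about simplified analyses partly covers the by-cohort change, and a comparison of about 12 against 6 is weak in any case. All of this stands and sets the severity. It does not settle which model is to be fitted.

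Several stronger readings are tempting, and the documents do not support them.

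- *The omission inflates false positives.* It does not. Shifting the test by the bias alone would suggest so, but the polyQ mix also enlarges the unadjusted SE, and two-sided size stays at or below 5%.
- *The bias undermines the reported conclusion.* It leans towards early start, and SAP Section 1 reports no clinical benefit. A lean in the drug's favour cannot explain that.
- *Leaving out the covariate departs from the protocol.* The protocol's own list is optional and does not name polyQ. Only the by-cohort change is a departure.
- *The model was left open after unblinding.* This SAP is dated 05 September 2024, and the integrated interim lock was April 29, 2024. However, Part 1 SAP Section 4.1 defers interim integrated analyses to a separate SAP, which is not available here and may have fixed the covariates.
- *The Early-start versus Delayed-start comparisons are listed key endpoints.* SAP Section 2.1 lists the endpoints, not these contrasts. The contrasts are set in Sections 5.6.1 to 5.6.5.
- *The log-rank test should be stratified by polyQ instead of NfL.* Protocol Section 13.3.5 itself names median NfL as the optional stratum, and the documents state no polyQ effect on survival. That swap would be a trade-off, not a correction.

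**Conclusion.** The concern holds as a minor point. The Week 40 ANCOVA for ALSFRS-R, SVC and HHD is inconsistently specified on a factor that defines the randomisation and that the protocol calls prognostic for ALSFRS-R and vital capacity. A committed by-cohort sensitivity analysis was also made optional without being declared.

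Without the term, the contrast leans towards early start by 0.01 to 0.08 SD, with unequal tails and no inflation of two-sided size. This rests on planned counts, since actual enrolment and Week 40 composition are not given, and on assumed residual polyQ shifts of 0.1 to 1 SD. No figure is claimed for HHD or survival. Confidence is high in the wording discrepancies; the numerical consequence is small.

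**What to change.** 1. Make ALS/polyQ status (D1 versus D2) a mandatory fixed factor in one integrated ANCOVA covariate list, and make the three descriptions in SAP Section 5.6.1 agree. This costs 1 degree of freedom and no new data. The SE is at most about 0.35% larger if polyQ has no effect, and smaller at assumed shifts of 0.25 SD or more.
2. Restore the commitment to D1-only and D2-only clinical function results from protocol Section 13.3.4, or declare the change in SAP Section 6 with one line of reason.
3. As a suggestion only, name ALS/polyQ among the optional Cox covariates in SAP Section 5.6.5. Leave the optional median-NfL log-rank stratum as it is.

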5.6.2. ALSFRS-R

General Description

The ALSFRS-R is a questionnaire to measure degree of impairment in 4 functional domains: respiratory function, bulbar function, gross motor skills, and fine motor skills. Each domain consists of 3 items, each scored from 0 to 4, with higher scores representing better function. The Each domain can have maximum score of 12 and the total possible score for ALSFRS-R is 48. The items for each domain are listed below.

- Respiratory function: dyspnea, orthopnea and respiratory insufficiency
- Bulbar function: speech, salivation and swallowing
- Gross motor skills: turning in bed, walking and climbing Stairs

CONFIDENTIAL

The information contained herein may not be used, disclosed, or published without the written consent of

Biogen MA Inc.

- Fine motor skills: handwriting, cut and handling utensils without or with gastrostomy, dressing and hygiene

General Considerations

Descriptive statistics for ALSFRS-R total score at each visit and their change from baseline will be summarized by treatment group. Corresponding plots will also be generated.

Descriptive analyses will be performed in the FAS population.

The total score is the sum of the 4 functional domain scores or all individual item scores if no missing item scores are present. Each domain score is the sum of scores of 3 items for that domain. For missing item scores, the total score and domain scores will be derived as described in the missing data section below.

Missing Data

A summary of missing data for ALSFRS-R total score will be presented based on observed data by treatment group and visit.

Missing data at each visit will not be imputed.

If there are missing data at item level, ALSFRS-R total and domain scores will be derived as below.

- The ALSFRS-R total score will be considered missing if more than 3 individual item scores are missing.
- If no more than 3 (≤ 3) individual item scores are missing and a functional domain has at least one individual item score available, the functional domain score with any missing item score(s) will be calculated by the following formula:

$$\text{ALSFRS-R domain score} = [(\text{average of all answered item scores}) \times 3].$$

The total score will be the sum of the 4 functional domain scores.

- If 3 individual item scores are missing from the same functional domain, then the ALSFRS-R domain score is considered as missing and the total score is calculated by the following formula:

ALSFRS-R total score = average of all answered item scores from other 3 domains x

Descriptive statistics

Descriptive statistics, including ALSFRS-R total and change from baseline in the ALSFRS-R total scores, will be evaluated by visit with descriptive statistics (mean, SD, median, 1st and 3rd quartiles, range) for pooled group DL and Part 2 BIIB105 60 mg in the FAS population.

Spaghetti plots will be presented by treatment group.

Statistical Analyses

The following analyses will be performed for pooled group DL in the FAS population.

CONFIDENTIAL

The information contained herein may not be used, disclosed, or published without the written consent of
Biogen MA Inc.

For integrated analyses of Part 1 and Part 2 for Cohorts D1 and D2, difference between treatment groups (i.e. Early-start BIIB105 120 mg and Placebo/Delayed-start BIIB105 120 mg) in least square means of Week 40 change from baseline with corresponding standard errors and 95% confidence intervals taken from the ANCOVA described in Section [5.6.1](#) based on the multiple imputation dataset.

5.6.3. HHD Megascore

General Description

Twenty-two muscles in 11 pairs are examined in both upper and lower extremities (left and right shoulder flexion, left and right elbow flexion, left and right elbow extension, left and right wrist extension, left and right abduction index finger, left and right abduction thumb, left and right abduction 5th digit, left and right hip flexion, left and right knee flexion, left and right knee extension, left and right ankle dorsiflexion).

Each muscle is tested at least twice. If the difference between the first two trials is greater than 15%, or if the evaluator thinks that one of the first two trials was not valid, a third trial may be performed. The maximum value of the two highest measures within 15% variability will be used for the analysis. If there is no pair with $\leq 15\%$ variability, then the maximum value of the two values that are closest together will be used for the analysis.

Missing Data

Missing data at each visit will not be imputed.

For any missing muscle strength with a reason of “UNABLE TO TEST”, the missing strength will be imputed as 0.

The megascore will be considered missing if more than 14 measures on individual muscles are missing. If no more than 14 (≤ 14) measures are missing out of 22 total measures, the megascore calculation steps for each subject at each visit steps are listed below:

- Calculate baseline mean and SD for each individual muscle from all subjects;
- Normalize results to Z-score for each subject at each visit for each individual muscle as:

$$Z - score = \frac{Observed\ result\ (muscle\ strength) - baseline\ mean}{baseline\ SD}$$

- Average Z-scores across all individual muscles to obtain the overall megascore for each subject at each visit.

Missing data of HHD megascore for postbaseline assessments will be imputed using the multiple imputation method as described in Section [5.6.1](#).

Descriptive Statistics

CONFIDENTIAL

The information contained herein may not be used, disclosed, or published without the written consent of Biogen MA Inc.

Descriptive statistics, including observed value and change from baseline in the HHD megascore, will be evaluated by visit with descriptive statistics (mean, SD, median, 1st and 3rd quartiles, range) for pooled group DL and Part 2 BIIB105 60 mg in the FAS population.

Spaghetti plots will be presented by treatment group.

Statistical Analyses

The following analyses will be performed for pooled group DL in the FAS population.

For integrated analyses of Part 1 and Part 2 for Cohorts D1 and D2, difference between treatment groups (i.e. Early-start BIIB105 120 mg and Placebo/Delayed-start BIIB105 120 mg) in least square means of Week 40 change from baseline with corresponding standard errors and 95% confidence intervals taken from the ANCOVA described in Section [5.6.1](#) based on the multiple imputation dataset.

